7.3 Data Analysis Plans

Main Trial

Our main statistical test for primary and secondary outcomes will be a Mantel-Haenszel chi-squared test, adjusted for recruitment site (FQHC). If there are important differences between the control and intervention arms across baseline variables known to be associated with the outcome being tested, we will also then use multiple logistic regression, adjusting for the additional baseline variables. One-sided tests will be used for the primary and secondary outcomes because we expect active interventions will lead to more favorable results compared to usual care.

7.3.1 Aim 1

For Aim 1, the main outcome of interest is the proportion of the sample completing FIT kits among those to whom the materials are mailed. We refer to this metric as the “proportion screened.” Using a 1:1 randomization approach, up to 2,000 RCCHC patients and up to 2,000 BRH patients will be randomized to each study arm (Arm 1-usual care; Arm 2-introductory letter + mailed FIT + 2 follow-up reminder letters).

Aim 1 analytic approach: Our primary analysis will be a crude comparison of proportions of completed CRC screening at 6 months post-FIT mailing for the mailed FIT plus reminder arm vs. the usual care arm using a one-sided Mantel-Haenszel chi-squared test, controlling for recruitment site (FQHC) and insurance status. As stated in the overview, we will also, if necessary, conduct a multiple logistic regression analysis. We will also compare the proportion screened between the mailed FIT plus reminder arm vs. the usual care arm for each of the four insurance status groups, using a one-sided Mantel-Haenszel chi-squared test, controlling for recruitment site, conducted at the 0.0125 significance level.

7.3.2 Aim 2

For Aim 2, we will examine intervention implementation outcomes, including the logistical feasibility, patient acceptability, and provider acceptability of a mailed FIT outreach program. To accomplish this aim, we will track and report feasibility and acceptability metrics. For feasibility, we will measure the proportion of bad addresses using the REDCap database. To assess patient acceptability and perceptions of program appropriateness, we will conduct semi-structured interviews with up to 30 patients who had a positive (abnormal) FIT result, were referred for follow-up colonoscopy, and were offered patient navigations services. Invitations will be made on a rolling basis until a sufficient number of patients complete the interviews. Invitation letters will be sent after no more than 6 months after the FIT kit was mailed. To assess acceptability and feasibility from the providers’ perspectives, we will conduct surveys and semi-structured interviews at two time points. For the interviews, the RCCHC or BRH medical director will send an email to the clinician listserv to invite clinicians at the target clinic to participate in a follow-up interview. If this approach does not yield enough clinician participants, UNC project staff will attend regularly scheduled provider meetings to enhance recruitment. Clinician interviews will be conducted in study months 6-12. We will also track and report the proportions of patients who inform us of ineligibility in response to the Introductory Letter and subsequent mailings.

Aim 2 analytic approach: For quantitative assessments, we will use descriptive statistics (e.g., proportions and associated 95% confidence intervals) to characterize feasibility and acceptability measures. For qualitative assessments (i.e., semi-structured interviews), we will perform a thematic analysis of transcribed interview data.

7.3.3 Aim 3

For Aim 3, the main outcome of interest is the total cost (sum of fixed and variable costs) and the incremental cost-effectiveness of the intervention arm versus the usual care arm, measured in cost per person screened for CRC. We will document all fixed and variable costs associated with implementing the intervention, based upon personnel time tracking, invoices, receipts paid, test kit and processing costs, postage and other mailing costs, and other means. Fixed costs (i.e., costs absorbed by the screening program irrespective of the number of participants screened) include those of program administration and setup, materials design, and database development and analytics. Variable costs (i.e., those that are determined by the number of participants engaged or screened) include the costs of the intervention materials, FIT kits, postage and mailing costs, and costs of patient navigation and other personnel involved in the screening and follow-up process. For personnel time (e.g., in-reach follow-up of non-responders; navigation to colonoscopy), we will record the amount of time in minutes spent on each participant interaction, and calculate cost by multiplying total time spent in minutes with the average hourly salary of participating clinic nurses, administrative staff, and other staff, as relevant. Time spent in training, handling samples, and data management will be monitored using a similar time-audit approach. Mailing-associated costs will be recorded for the intervention arm. We will also assess costs associated with additional health care utilization post-screening (e.g., follow-up colonoscopy). We will not assess fixed costs common across the arms, such as overhead operating costs of clinics, or costs related to the conduct of the study alone, such as costs associated with data collection. For secondary analyses using the societal perspective, we will also attempt to estimate patient time costs associated with the intervention arm versus usual care arm.

Aim 3 analytic approach: We will describe total costs associated with each of the intervention arms for the trial. We will then calculate the incremental cost-effectiveness ratio (ICER) defined as cost per additional person screened, comparing intervention arms to usual care. We will also perform sensitivity analyses to examine the effect of different prices (potentially negotiable for larger programs assuming volume-based economies of scale). For alternate analyses from the societal perspective, we will estimate patient time costs using the human capital method (Jonas et al., 2008).

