4.3.7 Number and Duration of Contact with Patients

4.3.7.1 CRC Screening

Patients in the Main Trial control arm (ages 50-75) will not be contacted. Patients in the Main Trial intervention arm (ages 50-75) and patients the Sub-study (ages 45-49) intervention arm and comparator arm will receive an Introductory Letter (first contact) that notifies the patient to expect a FIT kit in the mail. This mailing will allow the study team to identify patients with incorrect addresses before mailing the FIT kit.

After mailing the FIT kit (second contact), the study team will make up to two reminder attempts to follow up with patients in the intervention arm (Arm 2) who have not returned a completed FIT kit. If the FIT kit is undeliverable and returned to the study team because of an incorrect address, the patient will be removed from future Reminder Letter mailings.

Main Trial Patients (ages 50-75) in Arm 2 will receive up to two reminder letters (third and fourth contact). All sub-study patients (ages 45-49) in the intervention and comparator arms also will receive up to two reminder letters (third and fourth contact).

For patients who complete a FIT kit and have a negative result: The patient will be notified of the test result by letter (see section 4.3.5).

For patients who complete a FIT kit and have a positive (abnormal) result: The patients' primary care provider or the primary care provider's designee will notify the patient of the results. After the patient is notified of their positive result, the patient navigator (employed by UNC and credentialed by RCCHC and BRH) will contact the patient by phone or, if phone contact is not successful, by mail to offer information and support for accessing follow-up colonoscopy. Communication will include information about no-cost colonoscopy (for uninsured patients) and transportation service to and from the colonoscopy appointment (for all patients). The patient navigator will call the patient up to three additional times to support the patient in scheduling an appointment for a follow-up colonoscopy, preparing for the colonoscopy procedure, accessing transportation, and financial services, and understanding colonoscopy results. The approximate duration of each phone call will be 5-15 minutes.

The total number of contacts initiated by the study team will range from **3** (Introductory Letter + FIT kit mailing + results letter/call) to **9** (Introductory

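### Section 7.3.3 multiplies minutes by an hourly salary without dividing by 60, and leaves open whether that salary is pooled or role-specific

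*Combined protocol and SAP*

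**What the plan says.** Section 7.3.3 (Aim 3) of the combined protocol and SAP sets out how personnel time becomes a cost. On measurement: "we will record the amount of time in minutes spent on each participant interaction". On pricing, the team will "calculate cost by multiplying total time spent in minutes with the average hourly salary of participating clinic nurses, administrative staff, and other staff"; the sentence then closes with a short qualifier on relevance, quoted under the objection. The next sentence extends the time capture to other work: "Time spent in training, handling samples, and data management will be monitored using a similar time-audit approach".

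Labour enters the cost outcome through the variable costs, which include "costs of patient navigation and other personnel involved in the screening and follow-up process" alongside materials, FIT kits and postage. Total cost then feeds the "incremental cost-effectiveness ratio (ICER) defined as cost per additional person screened". Section 2.2 also puts the resources needed for statewide scale-up under Aim 3.

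The section states no division by 60, no wage, no total time and no labour cost, and no conversion appears elsewhere in the document. It does not say how an average salary would be formed or weighted.

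**The concern.** The two units in the pricing rule do not match. Minutes multiplied by dollars per hour do not give dollars until the minutes are divided by 60. This is the only personnel-cost formula in the plan, so anyone who programs it as written gets a wrong labour cost.

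A second, softer problem is the wage. The sentence lists several kinds of staff against a single average salary. The work is in fact mixed: project staff at the university build and mail the kits (Section 4.3.3), a university-employed navigator supports patients with a positive FIT, and the health centre's provider or a designee makes the results call (both Section 4.3.5). If one unweighted average were applied to all minutes, labour would be mispriced whenever pay and time shares differ by role. An error of that kind would look plausible and could pass into the cost per person screened and the scale-up estimate.

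**Working it through.** The plan states no labour cost, so there is no figure to reproduce. The check is one of units, with assumed wages for illustration.

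**Inputs from the plan.** Time is recorded in minutes and salary is hourly (Section 7.3.3). On navigation calls, Section 4.3.7.1 says: "The approximate duration of each phone call will be 5-15 minutes". The same section allows up to 4 navigation calls for a patient with a positive FIT.

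**Inputs assumed.** Hourly wages of $15 to $40 for step 1; $40 (nurse), $18 (administrative) and $25 (other) for step 3. The documents give none of these.

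**Step 1: units.** With T in minutes and W in dollars per hour:

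- Rule as written: C = T × W.
- Unit-consistent rule: C = (T / 60) × W.
- Ratio: (T × W) / (T × W / 60) = 60, for any T and W.

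For 4 calls × 15 minutes = 60 minutes:

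| Assumed wage | As written | Converted |
|---|---|---|
| $15/hour | 60 × 15 = $900 | $15 |
| $25/hour | 60 × 25 = $1,500 | $25 |
| $40/hour | 60 × 40 = $2,400 | $40 |

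**Step 2: reach of the factor.** If personnel time makes up a share s of the correctly computed total, the total as written is (1 − s) + 60s = 1 + 59s times the correct one. The factor is 60 for the personnel part alone and smaller for any total that has other components. The plan does not give s, so the effect on total cost or on the incremental ratio cannot be put as a number.

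**Step 3: pooled or role-specific salary, after conversion.** The unweighted pooled mean is (40 + 18 + 25) / 3 = $27.67/hour. The role-specific cost per hour is the sum over roles of time share × wage.

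| Time shares (nurse / administrative / other) | Role-specific, per hour | Pooled ÷ role-specific |
|---|---|---|
| equal thirds | $27.67 | 1.00 |
| 10% / 80% / 10% | 4.0 + 14.4 + 2.5 = $20.90 | 1.32 |
| 80% / 10% / 10% | 32.0 + 1.8 + 2.5 = $36.30 | 0.76 |
| administrative only | $18.00 | 1.54 |
| nurse only | $40.00 | 0.69 |

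Under these assumed wages an unweighted pooled mean can be too high or too low. There is no error if the time shares are equal, if the pooled mean is weighted by minutes, or if the averages are role-specific.

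**The case against.** The strongest reply is that this is a drafting slip. The sentence names both units, so the conversion it needs is evident, and $1,500 for an hour of telephone calls would be noticed at once. No reported figure is wrong, since none is reported. That is a fair reason to rate the point low. It does not make the rule right: this is analysis text, and it gives a wrong cost if followed.

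A reader might go further and infer that the plan averages salaries over all staff types and so misprices labour even after conversion. The text does not settle that. The sentence closes with "administrative staff, and other staff, as relevant", and the last two words can be read as meaning the average for whichever group did the work. Mispricing would need a pooled average not weighted by time, together with wages and time shares that differ by role. The documents establish none of these, and the direction would be unknown. What stands is an ambiguity.

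A reader might also infer that total cost or the incremental ratio would be 60 times too large, or that labour is a main cost of the intervention. The documents support neither. Personnel is one of several listed variable costs and no shares are given. Nor does the sentence on training, sample handling and data management apply the salary formula in terms; it describes how time is captured. Finally, the time log is not shown, so it cannot be said that the log lacks a field for role.

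**Conclusion.** Wrong as written; minor. The missing conversion is certain from the text, and the factor of 60 on personnel cost holds for any time and any wage, so it rests on no assumption. The dollar examples do rest on assumed wages. The choice between a pooled and a role-specific salary is unspecified rather than wrong; the range of 0.69 to 1.54 illustrates what an unweighted pooled mean could do under three assumed wages and does not predict what will happen. The point concerns Aim 3, a secondary objective. The screening comparison in Aim 1, the randomization and the sample size are unaffected.

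**What to change.** Replace the pricing rule in Section 7.3.3 with: personnel cost = sum over staff roles of (minutes worked by that role / 60) × that role's average hourly salary. State that the same formula is used wherever training, sample-handling and data-management time is costed. Confirm that the role of the person doing the work can be identified in the time log, either directly or from the activity recorded, and add a field if it cannot.

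The cost is one sentence in the plan and, at most, one field on the log. The log should be checked while time is still being recorded, because role may be hard to recover afterwards.

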7.3.4 Sub-study (ages 45-49)

Our main statistical test for outcomes 1 and 2 will be a Mantel-Haenszel chi-squared test. If there are important differences between the arms across baseline variables known to be associated with the outcome being tested, we will also then use multiple logistic regression, adjusting for the additional baseline variables.

7.4 Data Management/Audit

Study team members will enter data into separate REDCap databases. Study data will be stored securely and managed through the REDCap databases.

As an investigator-initiated study, the trial will also be audited by the Lineberger Cancer Center audit committee every six or twelve months, depending on the participation of affiliate sites.

8.0 STUDY MANAGEMENT

8.1 Institutional Review Board (IRB) Approval and Consent

It is expected that the IRB will have the proper representation and function in accordance with federally mandated regulations. The IRB should approve the consent form and protocol.

In obtaining and documenting informed consent, the investigator should comply with the applicable regulatory requirement(s), and should adhere to Good Clinical Practice (GCP) and to ethical principles that have their origin in the Declaration of Helsinki.

For mailed outreach participants (Main trial (ages 50-75) and sub-study (ages 45-49)): We will request a waiver of informed consent for mailed outreach participants because: 1) the research involves no more than minimal risk to the subjects; 2) the waiver will not adversely affect the rights and welfare of the subjects; and 3) the research could not practicably be carried out without the waiver.

For patient interview participants (patients 50-75): Before recruitment and enrollment onto this study, the patient will be given a full explanation of the study and will be given the opportunity to review the consent form. Each consent form must include all the relevant elements currently required by the FDA Regulations and local or state regulations. Once this essential information has been provided to the patient and the investigator is assured that the patient understands the implications of participating in the study, the patient will be asked to give consent to participate in the study by signing an IRB-approved consent form.

Prior to a patient's participation in the trial, the written informed consent form should be signed and personally dated by the patient and by the person who conducted the informed consent discussion. Patients aged 45-49 will not be invited to participate in interviews.

For provider survey participants: The online survey will include a study information page. Providers will indicate consent by proceeding to the online survey after reviewing the study information page. The brief survey asks providers to share their professional opinions about the mailed FIT outreach

program and implementation of CRC screening at their clinic. The questions do not request sensitive information.

For provider interview participants: We will request verbal consent only because we are inquiring about participants' jobs, not personal information about themselves.

8.2 Required Documentation

Before the study can be initiated at any site, the following documentation must be provided to the Clinical Protocol Office (CPO) at the University of North Carolina.

- A copy of the official IRB approval letter for the protocol and informed consent
- CVs and medical licensure for the principal investigator and any associate investigators who will be involved in the study
- A copy of the IRB-approved consent form

8.3 Registration Procedures

Please describe how you will keep track of patient enrollment.

8.4 Adherence to the Protocol

Except for an emergency situation in which proper care for the protection, safety, and well-being of the study patient requires alternative treatment, the study shall be conducted exactly as described in the approved protocol.

8.4.1 Emergency Modifications

UNC investigators may implement a deviation from, or a change of, the protocol to eliminate an immediate hazard(s) to trial subjects without prior UNC IRB approval.

For any such emergency modification implemented, a UNC IRB modification form must be completed by UNC Research Personnel within five (5) business days of making the change.

8.4.2 Single Patient/Subject Exceptions

Eligibility single subject exceptions are not permitted for Lineberger Comprehensive Cancer Center Investigator Initiated Trials under any circumstances. Other types of single subject exceptions may be allowed if proper regulatory review has been completed in accordance with Lineberger Comprehensive Cancer Center's Single Subject Exceptions Policy.

8.4.3 Other Protocol Deviations/Violations

According to UNC's IRB, a protocol deviation is any unplanned variance from an IRB approved protocol that:

- Is generally noted or recognized after it occurs

- Has no substantive effect on the risks to research participants
- Has no substantive effect on the scientific integrity of the research plan or the value of the data collected
- Did not result from willful or knowing misconduct on the part of the investigator(s).

An unplanned protocol variance is considered a violation if the variance meets any of the following criteria:

- Has harmed or increased the risk of harm to one or more research participants.
- Has damaged the scientific integrity of the data collected for the study.
- Results from willful or knowing misconduct on the part of the investigator(s).
- Demonstrates serious or continuing noncompliance with federal regulations, State laws, or University policies.

If a deviation or violation occurs please follow the guidelines below:

Protocol Deviations: UNC personnel will record the deviation in OnCore® (or other appropriate database set up for the study), and report to any sponsor or data and safety monitoring committee in accordance with their policies. Deviations should be summarized and reported to the IRB at the time of continuing review.

Protocol Violations: Violations should be reported by UNC personnel within one (1) week of the investigator becoming aware of the event using the same IRB online mechanism used to report UPIRSO.

Unanticipated Problems Involving Risks to Subjects or Others (UPIRSO):

Any events that meet the criteria for “Unanticipated Problems” as defined by UNC’s IRB (see section 6.1) must be reported by the Study Coordinator using the IRB’s web-based reporting system.

8.5 Amendments to the Protocol

Should amendments to the protocol be required, the amendments will be originated and documented by the Principal Investigator at UNC. It should also be noted that when an amendment to the protocol substantially alters the study design or the potential risk to the patient, a revised consent form might be required.

The written amendment, and if required the amended consent form, must be sent to UNC’s IRB for approval prior to implementation.

8.6 Record Retention

Study documentation includes all Case Report Forms, data correction forms or queries, source documents, Sponsor-Investigator correspondence, monitoring

logs/letters, and regulatory documents (e.g., protocol and amendments, IRB correspondence and approval, signed patient consent forms).

Source documents include all recordings of observations or notations of clinical activities and all reports and records necessary for the evaluation and reconstruction of the clinical research study.

Government agency regulations and directives require that all study documentation pertaining to the conduct of a clinical trial must be retained by the study investigator. In the case of a study with a drug seeking regulatory approval and marketing, these documents shall be retained for at least two years after the last approval of marketing application in an International Conference on Harmonization (ICH) region. In all other cases, study documents should be kept on file until three years after the completion and final study report of this investigational study.

